8.1 Participant Population

Participants who meet the inclusion and exclusion criteria will be eligible for participation in this study.

8.2 Inclusion Criteria

- Patients who have been mechanically ventilated for more than fourteen days.
- Clinically stable: oxygen saturation > 90% with a fractional inspired oxygen ≤ 0.40, external PEEP ≤ 5 cm H₂O, temperature ranging from 35.5 to 38.5°C, no intravenous administration of vasoactive agents.

8.3 Exclusion Criteria

- Patients in whom NMES does not elicit a palpable contraction of the abdominal muscles.
- Participants with broken or irritated skin on the abdominal wall.

- History of neuromuscular disease
- Body mass index $> 35 \text{ kg/m}^2$
- Patients who are not medically stable
- Participants with a pacemaker
- Female participants who are pregnant
- Patients under the age of 18
- Patients who are expected to die within four weeks
- Patients who are unable to follow verbal instructions
- Patients with epilepsy
- Patients with an abdominal wall hernia
- Patients with anoxic encephalopathy
- Patients with history of, or active, substance abuse

8.4 Patient Recruitment

The research team, including research nurses, principle investigator, and the associate investigators will be responsible for recruitment. Eligible participants will be informed of their eligibility by their clinician. Patients who are interested in taking part will be provided with an information sheet (attached) and advised to discuss the study in further detail with the investigators after taking adequate time to digest the information in the information sheet. Written informed consent will then be obtained from each participant before they take part in the study. However, because MV is a requirement for eligibility, participants will frequently be incapable of informed consent at the time of inclusion. In such cases, we will obtain informed consent from a legally authorized representative making decisions for eligible patients. As the participants recover, they will be evaluated for the capacity by their clinician and when they are deemed to have regained capacity they will be asked to provide informed consent to continue in the study.

Participation is entirely voluntary, with participation in no way affecting the care received. Patients will not be financially compensated in any way for participating in this study.

9 Study Treatments

9.1 Method of Assigning Participants to Treatment Groups

Up to 26 eligible patients will be randomly assigned to either active or placebo stimulation treatment groups in a 1:1 ratio using a computer generated random sequence.

9.2 Blinding

The difference between active and placebo stimulation can be distinguished visually as active stimulation causes a tetanic muscle contraction whereas placebo stimulation causes a sub-tetanic muscle contraction. Therefore study personnel who apply the treatment to subject will not be blinded to study patients' treatment group assignment.

The following procedures will be used to ensure that patients are blinded to the treatment group that they have been assigned to:

- Study personnel will be instructed not to inform patients as to whether a tetanic or twitch contraction is the active or placebo treatment arm of the study.
- The appearance of the active and placebo stimulation devices will be identical.

In addition, all clinical staff not involved in the study and all study personnel who do not apply stimulation to patients will be blinded to the treatment group assignment of participants. This measure will help ensure that decisions to attempt weaning are unrelated to the study and are only based on clinical care.

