9.5 Packaging and Labeling of the Study Devices

Placebo and active stimulators will be able to be distinguished using a colored sticker, placed on the bottom of the device, with the meaning of each color identifiable only to the research team.

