9.6 Device Administration

In both of the study arms (active and placebo stimulation), stimulation will be administered for thirty minutes, twice per day, 5 days per week for the shorter of six weeks or until the patient is weaned from mechanical ventilation by one of the two trained study researchers.

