11.15 Measures of Treatment Compliance

The study treatment devices will automatically record the date, time and duration of stimulation for an individual patient to a memory card.

12 Study Schedule

A Schedule of Events representing the required testing procedures to be performed for the duration of the study is diagrammed in Appendix 1. A description of each procedure is provided in Section 11

Prior to conducting any study-related activities, written informed consent and the Health Insurance Portability and Accountability Act (HIPAA) authorization must be signed and dated by the participant.

12.1 Baseline Visit - Day 1

On day 1 the investigators will review the study with the participant and obtain written informed consent and HIPAA authorization. After consent has been obtained they will record the patient's demographic data, medical history and concomitant medications.

The investigators will determine if the patient meets the study inclusion and exclusion criteria. If the patient does not meet the criteria then no further procedures will be performed and they will be withdrawn from the study. If the patient does meet the criteria then the investigator will randomize the patient to a treatment group.

The study researcher will record their vital signs, oximetry, expiratory flow limitation, APACHE II score, MIP, MEP, thickness of the abdominal wall muscles and diaphragm, CPF and resting breathing parameters.

12.2 Stimulation Visits – Days 2 - 22

Patients will participate in Stimulation Visits two 2 per day in 5 days every week. Specifically, patients will participate in morning and afternoon Stimulation Visits 5 times between days 2 and 8, 5 times between days 9 and 15 and 5 times between days 15 and 22.

The investigators will administer sixty minutes of stimulation to the participant as described in Section 9.6. In addition, the investigators will record adverse events related to stimulation or otherwise.

12.3 Intermediate Visit – Day 23

The Intermediate Visit will ideally take place on day 21. However, if necessary the Intermediate Visit may be conducted no earlier than day 20 and no later than day 25, providing that it occurs after 15 Stimulation Visits.

At the start of the visit the investigators will measure MEP, MIP, CPF, thickness of the abdominal wall muscles and diaphragm, resting breathing parameters, changes to medications and adverse events related to stimulation or otherwise.

12.4 Stimulation Visits – Days 24 – 44

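### The plan requires no blinded assessor for MIP and MEP, and it gives stimulation and measurement to the same role labels

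*Combined protocol and SAP*

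**What the plan says.** Section 9.2 explains that the two kinds of contraction can be told apart by eye and concludes that "study personnel who apply the treatment to subject will not be blinded". It adds that "all study personnel who do not apply stimulation to patients will be blinded to the treatment group assignment of participants". The only purpose it gives for blinding staff concerns weaning: "This measure will help ensure that decisions to attempt weaning are unrelated to the study". It does not mention measurement of outcomes.

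Section 9.6 has stimulation given "by one of the two trained study researchers", while 12.2 says: "The investigators will administer sixty minutes of stimulation to the participant as described in Section 9.6". At baseline (12.1), "The study researcher will record their vital signs, oximetry, expiratory flow limitation, APACHE II score, MIP, MEP". At the Intermediate, Final and Early Withdrawal visits (12.3, 12.5, 12.6) the investigators measure or record MEP and MIP.

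Section 9.5 distinguishes the stimulators by a coloured sticker, "with the meaning of each color identifiable only to the research team". Section 8.4 describes that group, in the context of recruitment, as "The research team, including research nurses, principle investigator, and the associate investigators". In 12.1 the investigator randomises the patient on Day 1, and the baseline measurements are listed after that step.

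Section 7.1 makes MIP and MEP the primary outcome. Section 11.9 cites a published method for them but names no assessor and sets out no blinding, number of attempts or coaching script. The synopsis and Section 6 describe the trial as participant blinded and claim no assessor blinding.

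**The concern.** MIP and MEP are maximal voluntary tests. The documents do not call them effort-dependent. It follows from the word maximum, and it fits with the exclusion of patients who cannot follow verbal instructions (8.3). In such a test the assessor prompts the patient and decides when an attempt is good enough. If the assessor knows the arm, encouragement can differ between arms and the difference enters the primary comparison. Nothing in Section 17 is designed to detect or adjust for it.

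This matters even in a pilot. Section 5 states the primary objective as finding out whether stimulation increases respiratory muscle strength, and Section 17 plans between-group tests and regression models. Cough peak flow and the ultrasound thickness measurements are assigned to the same roles.

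**Working it through.** **Step 1: who does what.**

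| Task | Section | Role named |
|---|---|---|
| Stimulation | 9.6 | one of two trained study researchers |
| Stimulation | 12.2 | the investigators |
| Randomisation, Day 1 | 12.1 | the investigator |
| MIP/MEP, Baseline | 12.1 | the study researcher |
| MIP/MEP, Intermediate | 12.3 | the investigators |
| MIP/MEP, Final | 12.5 | the investigators |
| MIP/MEP, Early Withdrawal | 12.6 | the investigators |

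At every visit where the primary outcome is taken, the role named is one that the plan elsewhere names as delivering stimulation. The Early Withdrawal row matters because 14.1 lists successful weaning as a reason for discontinuation, so participants who wean early would have their end measurement there.

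**Step 2: who can know the allocation.** Section 9.2 blinds study personnel who do not stimulate. Section 9.5 lets the research team as a whole read the colour code, without limiting it to those who stimulate. Under 12.1 the investigator randomises, and may therefore know the arm without ever handling a device. Read literally, the three sections do not yield a defined group of blinded staff. Because randomisation is listed before the baseline tests, the baseline value may also be measured with the arm known.

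**Step 3: illustration of size.** The plan has no figure for this. The inputs from the plan are 12 per arm (Section 6; 24 in total in 17.1) and 1:1 allocation (9.1). For context, 24 / (1 − 0.10) = 26.7 against the 26 to be recruited, which is close and does not bear on this point. The remaining inputs are assumptions: two-sided alpha of 0.05, no true effect, and a shift δ in SD units caused only by the assessor. The calculation is for one measure and uses an equal-variance t-test.

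Noncentrality = δ × √(n/2). For n = 12, √6 = 2.449, and the critical value of t on 22 degrees of freedom is 2.074. The false-positive rate is the probability that the noncentral t falls beyond ±2.074. The chance that the estimate favours active is Φ(noncentrality).

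| δ (SD, assumed) | Noncentrality, n = 12 | False-positive rate, 12 per arm | False-positive rate, 13 per arm | Estimate favours active, 12 per arm |
|---|---|---|---|---|
| 0 | 0 | 5.0% | 5.0% | 50% |
| 0.2 | 0.490 | 7.6% | 7.8% | 69% |
| 0.3 | 0.735 | 10.8% | 11.4% | 77% |
| 0.5 | 1.225 | 21.6% | 23.2% | 89% |

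**Step 4: extent of the scheduling constraint.** MIP and MEP are scheduled at three visits (Days 1, 23 and 45), with Early Withdrawal in place of a later one. Stimulation sessions number up to 2 per day × 5 days × 6 weeks = 60 per participant.

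**The case against.** The strongest reply is that the overlap is inferred from labels. The labels are used loosely: 9.6 gives delivery to study researchers and 12.2 gives it to the investigators. A reader might infer that the very people who stimulate a participant will also measure that participant's MIP and MEP. No sentence says so, and a blinded colleague could do it without breaching the plan. This part of the reply stands. What remains is that nothing requires a blinded assessor.

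A reader might also infer from 9.2 and 8.4 that trained, blinded assessors are ready to use. The documents do not show that. Section 8.4 lists nurses and investigators as recruiters. No section says how many staff stay blinded, or that they are trained in cannula pressures or ultrasound.

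It is fair to add that the trial claims only participant blinding, and that 17.1 describes a pilot for initial feasibility and safety data without a power calculation. A false-positive rate weighs less there than in a confirmatory trial. The method cited in 11.9 may also standardise the manoeuvre; the plan itself does not say. Being able to decode a sticker is also not the same as having seen the device used for a given participant. These points lower the weight of the concern but do not supply the missing requirement.

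Finally, unblinding the staff who stimulate is justified by the visible contraction and is not criticised here.

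**Conclusion.** The point holds as a gap in the plan. No blinded assessor is required for the primary outcome, delivery and measurement fall to the same role labels, and Sections 9.2, 9.5 and 12.1 need to be reconciled on who may know the allocation. Following the plan as written could bias MIP and MEP.

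The documents do not show that such bias will occur or how large it would be. The range of 7.6% to 21.6% false positives rests wholly on an assumed shift of 0.2 to 0.5 SD, an assumed two-sided 5% level and 12 per arm. It shows what is at stake and is not an estimate. This is a cheap improvement to the design: the sample size, the treatment and the visit days stay as they are.

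**What to change.** - In 9.2, 11.9 to 11.12 and 12.1 to 12.6, assign MIP, MEP, cough peak flow and ultrasound to existing study personnel who do not apply stimulation, the group that 9.2 already says is blinded.
- In 9.5, restrict the colour key, and likewise the allocation list, to those who deliver stimulation or hold the randomisation. Whoever randomises under 12.1 should not be an assessor.
- In 12.1, take the baseline MIP and MEP before the allocation is revealed.

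The cost is a scheduling constraint on about three assessment visits per participant, plus training of the blinded staff if they lack the measurement skills. Restricting the key and reordering Day 1 need only a change of text and procedure.

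Using the second trained researcher as assessor is possible but dearer. That person would have to stay out of all of that participant's stimulation sessions, up to 60, and be kept from the colour key and allocation for that participant. With only two trained researchers, this reduces cover for absence.

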9.3 Active and Placebo Study Devices

The VentFree prototype (model: VF03-K) will be used for both the active and placebo devices. The active stimulation device's stimulation parameters will be set to cause a tetanic contraction of the abdominal muscles, whereas the placebo stimulation device's stimulation parameters will be set to cause a twitch contraction of the abdominal muscles. All other device parameters will be identical between the two types of devices. The relevant stimulation parameters will be locked on each device so that it is not possible to accidentally change the parameters that distinguish the active devices from the placebo devices.

9.3.1 Active Stimulation Device

The active devices will use the stimulation parameters that were used during Liberate's previous prospective clinical trials. Specifically:

- Stimulation frequency = 30 Hz
- Stimulation pulse width = 350 μ s
- Stimulation current = 90 % of the participants tolerated maximum (see Administration Instructions, Section 9.6).
- Stimulation delay = 0.1 seconds after the start of exhalation.
- Stimulation ratio – The stimulation ratio, which determines the duration of stimulation during exhalation as a fraction of the duration of the proceeding inhalation, will initially be set to 0.8. If the study researcher observes that stimulation does not last for the duration of exhalation, then he or she will increase the stimulation ratio. Similarly, if the study researcher believes that the duration of stimulation is too short then he or she will reduce the stimulation ratio.

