4.1 Study Device

This study will use the VentFree prototype (model number: VF03-K) that consists of a commercially available and FDA cleared neuro muscular electrical stimulator (Continuum, Empi, USA) and a stimulation trigger (designed by Liberate Medical). The disposable components of the device are single patient use and include two sets of 4 cm by 5 cm rectangular stimulation electrodes (PALS Platinum) and a variable orifice pneumotachograph (Braebon). A picture of the device is shown in **Error!**

[figure not shown]

Figure 2 VentFree picture
Reference source not found..

The main features of the device are:

- **Exhalation synchronized stimulation to the abdominal wall muscles –** the device allows the timing and duration of the stimulation burst as well as the parameters of the stimulation pulses to be modified by the user.

- **Expiratory flow limitation test** – this mode of the device records the output of the respiratory sensor for the purposes of conducting an expiratory flow limitation test (see Section 11.8).
- **Compliance monitoring** – the time, date and the duration of each stimulation session is recorded by the device.

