9.3.2 Placebo Stimulation Device

The placebo devices will use a stimulation frequency of 10 Hz, a stimulation pulse width of 100 μ s and a stimulation current of 10mA. The stimulation ratio will be set to 0.8 for all subjects. All other parameters will be set according to the active stimulation device.

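### Section 9.3.1 gives opposite instructions for adjusting the active-arm stimulation ratio when stimulation is too short

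*Combined protocol and SAP*

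**What the plan says.** Section 9.3.1 of the combined protocol and SAP says that the stimulation ratio "determines the duration of stimulation during exhalation as a fraction of the duration of the proceeding inhalation, will initially be set to 0.8". The word before inhalation is read here as meaning the preceding one. The same list gives "Stimulation delay = 0.1 seconds after the start of exhalation".

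Two adjustment instructions follow, joined by a word that presents the second as parallel to the first:

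- "If the study researcher observes that stimulation does not last for the duration of exhalation, then he or she will increase the stimulation ratio"
- "if the study researcher believes that the duration of stimulation is too short then he or she will reduce the stimulation ratio"

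For the placebo arm, section 9.3.2 says: "The stimulation ratio will be set to 0.8 for all subjects". It contains no adjustment instruction.

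On recording, section 11.15 says: "The study treatment devices will automatically record the date, time and duration of stimulation for an individual patient to a memory card". Section 4.1, describing the same compliance feature, refers to the duration of each session. Neither section mentions the ratio in use.

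**The concern.** A burst that stops before exhalation is over is, in ordinary language, too short. Section 9.3.1 appears to describe that situation twice and to prescribe opposite responses. The situation in which a reduction would lengthen nothing but might be expected, stimulation that lasts too long, is not mentioned.

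Burst duration per breath is part of the delivered active treatment. Section 9.6 has stimulation given by one of two researchers, twice a day, 5 days a week, for up to 6 weeks, which is at most 2 × 5 × 6 = 60 sessions per participant. If the researchers read the rule differently, or one researcher reads it differently on different days, active participants could receive different amounts of stimulation per breath for reasons unrelated to their condition. In a pilot with 13 participants per arm, that would make the estimated effect on respiratory pressures harder to interpret, and a null result especially so. If the ratio is not recorded, the analyst could not see that this had happened.

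**Working it through.** The plan states no figure to reproduce here. The main check is a comparison of the text, followed by two short calculations that are illustrative only.

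**1. The two sentences against the definition**

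From the definition in section 9.3.1, with D the burst duration, r the ratio and Ti the inhalation time: D = r × Ti. Lowering r therefore shortens the burst, and raising r lengthens it.

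| | Trigger | Action on r | Effect on D |
|---|---|---|---|
| First sentence | Burst ends before exhalation ends | Increase | Longer |
| Second sentence | Burst judged too short | Reduce | Shorter |
| (none) | Burst too long | Not stated | Not stated |

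The first row moves D toward removing its trigger. The second row moves D further into its trigger. This holds even for a reader who thinks the two triggers are not quite the same observation, because the second instruction works against its own stated reason.

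**2. Does another section settle it?**

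- Section 4.1 says that "the device allows the timing and duration of the stimulation burst" can be modified by the user, along with the pulse parameters. It gives no direction.
- Section 9.6.2 has the operator check the timing settings at setup but gives no target.
- Section 9.6.3 describes how the current is set, not the ratio.
- The device's instructions for use, mentioned in section 9.6.2, are not among the documents.

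None of these resolves the conflict.

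**3. Could the trigger be met at the starting setting? (assumed breathing pattern)**

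Stimulation starts 0.1 s into exhalation and lasts 0.8 × Ti. With Te the exhalation time, it ends early when Te > 0.1 + 0.8 × Ti. The documents give neither Ti nor Te. The assumed range is 15, 20, 25, 30 and 35 breaths per minute, with Te/Ti of 1, 1.5, 2 and 3, which makes 5 × 4 = 20 combinations.

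The tightest case is 35 per minute with Te/Ti = 1. The breath lasts 60/35 = 1.71 s, so Ti = Te = 0.86 s. The burst ends at 0.1 + 0.8 × 0.857 = 0.79 s, before 0.86 s. The burst ends early in all 20 combinations.

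The share of exhalation stimulated is 0.8 / (Te/Ti):

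- Te/Ti = 1: 80%
- Te/Ti = 1.5: 53%
- Te/Ti = 2: 40%
- Te/Ti = 3: 27%

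Under these assumptions the first trigger is met before any adjustment. This shows how readily the conflict can arise; it says nothing about what the ratio should be.

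**4. How far apart could the two instructions take the burst? (assumed step)**

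With one step s taken up by one operator and down by another from 0.8, Ti cancels and the ratio of set burst durations is (0.8 + s) / (0.8 − s).

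- s = 0.1: 0.9 / 0.7 = 1.29
- s = 0.2: 1.0 / 0.6 = 1.67

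Both step sizes are assumptions; the documents give none.

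**The case against.** The best reply is that this is a drafting slip with little practical reach. The linking word, and the absence of any sentence for an over-long burst, suggest that one word in the second sentence is wrong. Only two researchers deliver treatment, both trained by the principal investigator, and the instructions for use may state the rule clearly. This is plausible, and it means that divergence between operators cannot be presumed. It does not remove the conflict: the protocol is the governing text, it does not show which wording was intended, and the instructions are not available to check.

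Three stronger readings are tempting, and the documents do not support them.

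- *The active treatment as a whole is undefined.* It is not. Frequency, pulse width, delay, initial ratio, the method of setting current, session length and schedule are all stated. Only burst duration per breath after the initial setting is unclear.
- *The fixed placebo ratio contradicts section 9.3*, which says: "All other device parameters will be identical between the two types of devices". That sentence follows a statement that the stimulation parameters differ between arms. Section 9.3.1 lists the ratio among the stimulation parameters, and section 9.3.2 openly sets a placebo value for it alongside frequency, pulse width and current. The ratio can fairly be placed among the parameters allowed to differ, so a contradiction is not established.
- *Adjusting the ratio in the active arm only is itself a flaw.* Current is also individualised in the active arm and fixed at 10 mA in placebo. An individually set treatment against a fixed low-level control is the stated design, and section 9.2 already says that those applying stimulation are not blinded.

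It is also fair to say that the fold differences rest on assumed steps and are not linked to the primary pressures. That objection stands.

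**Conclusion.** The point holds as an internal contradiction in an operative delivery rule. In the active arm, section 9.3.1 sends too-short stimulation in two directions, and its second instruction, followed literally, shortens a burst already judged too short. What is left unclear is burst duration per breath after the starting value of 0.8, and nothing wider.

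The size of the effect on the trial cannot be derived from the documents. The 1.29-fold and 1.67-fold differences in burst duration assume one step of 0.1 or 0.2 in each direction. The finding that bursts end early at the starting setting assumes 15 to 35 breaths per minute and Te/Ti of 1 to 3. Neither calculation is evidence of bias in maximum inspiratory or expiratory pressure. The contradiction itself rests on no assumption beyond the protocol's own definition of the ratio.

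**What to change.** The sponsor should reconcile the two adjustment sentences in section 9.3.1 so that each observation leads to one stated adjustment, and should make sure that the instructions for use and researcher training agree with the reconciled text. Which adjustment belongs to which observation is for the sponsor to decide; none is proposed here.

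The ratio in use should also be recorded at each session, including any change made during it, and summarised for the active arm. The stated device log does not cover this, and without it the delivered burst duration may not be recoverable at analysis.

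The cost is one correction to protocol wording and one extra field on the session form. No change to the design, sample size or planned analyses is needed.
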